6.4.5. Physical Examinations

A full physical examination will be performed at the Screening visit (according to standard medical practice, including assessment of height and weight). Symptom-directed physical examinations will be performed at all other scheduled timepoints. Interim physical examinations may be performed at the discretion of the Investigator. Any clinically significant finding identified by an HCP during study visits should be reported as a MAAE.

Physical examination results will be presented in a data listing.

6.5. Immunogenicity Analysis

The analyses of immunogenicity will be based on the PP Set. If the number of participants in the FAS and PP Set differs (defined as the difference divided by the total number of participants in the PP Set) by more than 10%, supportive analyses of immunogenicity may be conducted using the FAS.

6.5.1. Immunogenicity Assessments

Blood samples for humoral and cellular immunogenicity assessments will be collected at the timepoints specified in Table 1 in the protocol. The following analytes may be measured:

- Serum antibody level as measured by HAI assay.
- Serum antibody level as measured by MN assay or similar method, if necessary.
- Virus-specific B-cell responses measured by flow cytometry or other methods, and targeted repertoire analysis of B cells after vaccination.

Analytes may be measured using other exploratory serological assays and cellular immunogenicity assays.

6.5.2. Immunogenicity Analysis

The following immunogenicity endpoint will be evaluated:

- GMT and GMFR, comparing Day 29 with Day 1 (baseline), and percentage of participants with seroconversion, defined as a postbaseline titer $\geq 1:40$ if baseline is

<1:10 and a 4-fold or greater rise if baseline is $\geq 1:10$ in anti-HA antibodies measured by HAI assay.

For the immunogenicity endpoints, the geometric mean (GM) of specific antibody titers with corresponding 95% CI at each timepoint and the GMFR of specific antibody titers with the corresponding 95% CI at each post-baseline timepoint over pre-injection baseline at Day 1 will be provided by vaccination group. For each vaccination group, all influenza strains will be tested.

Descriptive summary statistics, including median, minimum, and maximum, will also be provided. The GM will be calculated using the following formula ([Nauta 2011](#)):

$$2^{\left\{ \frac{\sum_{i=1}^n \log_2(t_i)}{n} \right\}}$$

where t_1, t_2, \dots, t_n are n observed immunogenicity titers or levels.

The GMFR measures the changes in immunogenicity titers or levels within participants. The GMFR will be calculated using the following formula:

$$2^{\left\{ \frac{\sum_{i=1}^n \log_2(v_{ij}/v_{ik})}{n} \right\}} = 2^{\left\{ \frac{\sum_{i=1}^n \log_2(v_{ij}) - \log_2(v_{ik})}{n} \right\}}$$

where, for n participants, v_{ij} and v_{ik} are observed immunogenicity titers or levels for participant i at timepoints j and $k, j \neq k$.

The 95% CIs for GMT and GMFR will be calculated based on the t distribution of the log-transformed values then back transformed to the original scale for presentation, unless otherwise specified.

For summarizations of GMT and GMFR, antibody titers reported as below LLOQ will be replaced by $0.5 \times \text{LLOQ}$. Values that are greater than the ULOQ will be converted to the ULOQ.

The model-based GM titer will be estimated based on an analysis of covariance (ANCOVA) model. In the ANCOVA model, the log-transformed antibody titer at the post-baseline timepoint (Day 29) will be treated as the dependent variable with the vaccination group as the explanatory variable and influenza vaccination status in the previous influenza season (received or not received) and the log-transformed baseline antibody titer as the covariates.

The GMT will be estimated by the geometric least square mean (GLSM) from the ANCOVA model for each vaccination group and corresponding 95% CI will be provided.

For each between-group comparison in Table 6, the GMTR (i.e. ratio of GMTs) between the two vaccination groups at Day 29 will be estimated from the ANCOVA model, with 95% CI provided accordingly.

Seroconversion rate from baseline will be provided with a 2-sided 95% CI using the Clopper-Pearson method at each post-baseline timepoint. For HA, the rate of seroconversion is defined as the proportion of participants with either a pre-vaccination HAI titer < 1:10 and a post-vaccination HAI titer \geq 1:40 or a pre-vaccination HAI titer \geq 1:10 and a minimum 4-fold rise in post-vaccination HAI antibody titer.

For each between-group comparison specified in Table 6, the difference of seroconversion rates between the two vaccination groups at Day 29 for each applicable pair will be provided along with 95% CIs estimated using Miettinen-Nurminen method.

Table 6: Between-Group Immunogenicity Comparisons

Control Arm	Treatment Arm			
	mRNA-1011.1 50 μ g	mRNA-1011.2 40 μ g	mRNA-1012.1 50 μ g	mRNA-1012.1 62.5 μ g
mRNA-1010 (Darwin) 50 μ g	X	X	X	X
mRNA-1010.2 (Newcastle) 50 μ g	X	X	X	X
mRNA-1010.3 (Hong Kong) 50 μ g	X	X	X	X
mRNA-1011.2 40 μ g	X	NA	X	X

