## 4.2. Scientific Rationale for Study Design

This study will enroll healthy adults aged  $\geq 50$  to  $\leq 75$  years to evaluate next-generation influenza mRNA vaccine candidates. This broad age range allows inclusion of older adults who often have higher risk of comorbidities and conditions that could lead to more negative health outcomes due to influenza. mRNA-1011.1, mRNA-1011.2, and mRNA-1012.1 could provide a public health benefit through increasing protection against circulating influenza A/H3N2 strains.

The additional H3N2 strains evaluated in this study were selected by the Sponsor for their antigenic distance compared to the Darwin strain contained in the 2022/2023 NH vaccine composition and greater antigenic breadth across the H3N2 virus family. Due to WHO reporting

limited circulation of the B/Yamagata virus in recent years, the mRNA-1011.1 and mRNA-1012.1 candidates were designed to not contain the B/Yamagata HA, allowing for higher proportion of other strains/additional strains to be represented in the vaccine. Data from this study will help distinguish the immune responses against the respective vaccine strains, using the HAI assay, and evaluate the added benefit of mRNAs encoding additional influenza A/H3N2 strains from the WHO recommended strains. The Sponsor expects to follow public health recommendations for inclusion of multiple H3N2 strains once such recommendations are available.

The study will be conducted in an open-label manner. Since all study arms will receive DP in a relatively narrow dosage range that have the same clinical indication, developed with the same technology platform (mRNA platform) and there is no placebo arm, the preference or bias for particular study products would be perceived to be minimum from either investigators' or participants' perspective.

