### **9.5.3. Immunogenicity Analyses**

The analyses of immunogenicity will be based on the PP Set. If the number of participants in the FAS and PP Set differ (defined as the difference divided by the total number of participants in the PP Set) by more than 10%, supportive analyses of immunogenicity data may be conducted using the FAS.

For the immunogenicity endpoints, GM of specific antibody titers with corresponding 95% CI at each timepoint and GMFR of specific antibody titers with corresponding 95% CI at each postbaseline timepoint over preinjection baseline at Day 1 will be provided by treatment arm. Descriptive summary statistics including median, minimum, and maximum will also be provided.

For summarizations of GMTs, GMFR, antibody titers reported as below LLOQ will be replaced by  $0.5 \times \text{LLOQ}$ . Values that are greater than the ULOQ will be converted to the ULOQ.

Seroconversion rate from baseline will be provided with a 2-sided 95% CI using the Clopper-Pearson method at each postbaseline timepoint. For HA, rate of seroconversion is defined as the proportion of participants with either a prevaccination HAI titer  $<1:10$  and a postvaccination HAI titer  $>1:40$  or a prevaccination HAI titer  $>1:10$  and a minimum 4-fold rise in postvaccination HAI antibody titer.

GMTRs with corresponding 95% CI will be calculated for each candidate vaccine group against matched mRNA-1010 controls (mRNA-1010, mRNA-1010.2 and mRNA-1010.3) after adjustment of baseline titers, at each available timepoint.

Further details will be described in the SAP.

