6.6. Exploratory Analyses

The below exploratory analyses of immunogenicity may be performed:

- GMT, GMTR (mRNA-1011.1, mRNA-1011.2, and mRNA-1012.1 against mRNA-1010), and GMFR (compared with Day 1) of anti-HA as measured by HAI assay.
- GMT and GMFR (compared with Day 1) of anti- HA antibodies as measured by MN assays or other alternative methods against vaccine matched strains.
- GMT and GMFR (compared with Day 1) of anti- HA antibodies as measured by HAI or MN assays against vaccine-mismatched strains.

- Frequency, magnitude, and phenotype of virus-specific B-cell responses measured by flow cytometry or other methods, and to perform targeted repertoire analysis of B cells after vaccination.
- Frequency of RT-PCR-confirmed ILI and assessment of immune responses in participants with RT-PCR-confirmed ILI.

In the ANCOVA model, the log-transformed antibody titers at each available post-baseline timepoint (Day 29 and Day 181/EoS) are treated as the dependent variable, with the treatment group as the explanatory variable and influenza vaccination status in the previous influenza season (received or not received) and the log-transformed baseline antibody titer as the covariates.

An NP swab specimen for viral respiratory pathogens will be collected prior to the study intervention administration on Day 1. Throughout the study, the participant will be instructed to contact the study site if he/she has symptoms suggestive of ILI. An unscheduled visit for symptom assessment and NP swab for viral respiratory pathogens will be conducted if a participant has protocol-defined ILI ≤ 7 days of symptom onset.

The frequency of RT-PCR-confirmed ILI, including RT-PCR-confirmed protocol-defined influenza infection and RT-PCR-confirmed CDC-defined influenza infection, is an exploratory efficacy endpoint. A participant may have multiple RT-PCR results for influenza post-baseline and is counted as positive if the participant had at least one positive post-baseline result for influenza. The following outputs will be provided for RT-PCR-confirmed ILI based on the FAS:

- The number and percentage of participants with negative, positive, and inconclusive/invalid RT-PCR test results for influenza at baseline and post-baseline will be summarized by vaccination group.
- Participants with baseline and post-baseline positive RT-PCR results for influenza will be presented in a listing.

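### A single ANCOVA per strain over all seven arms gives the matched-control GMTR intervals their stated 95% coverage for four of the six strains only if arms with and without the strain have the same residual scatter.

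*SAP*

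**What the plan says.** SAP 6.5.2 gives one ANCOVA form. The log Day 29 titer is the dependent variable, "with the vaccination group as the explanatory variable and influenza vaccination status in the previous influenza season" and the log baseline titer as covariates. Group means come from it: "The GMT will be estimated by the geometric least square mean (GLSM) from the ANCOVA model for each vaccination group". So do the comparisons: "the GMTR (i.e. ratio of GMTs) between the two vaccination groups at Day 29 will be estimated from the ANCOVA model", for every pair marked in SAP Table 6. Every serum is assayed against every strain: "For each vaccination group, all influenza strains will be tested". SAP 6.6 repeats the model for Day 29 and Day 181, again "with the treatment group as the explanatory variable".

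No text restricts a strain's model to the arms that encode it, adds a group-by-baseline term, or allows the residual variance to differ by arm. Nor does any text state outright that all seven arms enter each fit. That is the natural reading of a single model that yields a mean for each group.

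The comparisons of most interest are the matched ones. Protocol 9.5.3 says: "GMTRs with corresponding 95% CI will be calculated for each candidate vaccine group against matched mRNA-1010 controls".

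**The concern.** Protocol Table 3 (SAP Table 1) shows that only A/H1N1 and B/Victoria are in all seven vaccines. For the other four strains, a seven-arm model mixes arms that received the antigen with arms that did not. An arm that mounts little response to a strain should largely reproduce its baseline titers at Day 29. An arm that responds carries the between-person spread of that response. If so, the common residual variance is lower than the variance in the two encoding arms being compared, and their GMTR interval is too narrow.

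The study has no hypothesis test, so estimates and intervals are its main immunogenicity evidence, and the protocol says that the data are to support selection of a lead candidate. Hong Kong is the most exposed strain. It is encoded only by mRNA-1012.1 (two dose levels) and mRNA-1010.3, so four of the seven arms feeding its error term never received it.

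**Working it through.** **Plan's own figure.** The documents state no precision figure for a GMTR. The only sample-size figures are adverse-event probabilities, which have no bearing on this point.

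**Step 1. Which arms encode which strain** (Protocol Table 3):

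| Strain | Encoding arms | Non-encoding arms | Matched candidate-control pairs |
|---|---|---|---|
| A/H1N1, B/Victoria | 1-7 | none | not affected |
| B/Yamagata | 1, 5, 6, 7 | 2, 3, 4 | 3 |
| Darwin | 1-5 | 6, 7 | 4 |
| Newcastle | 1-4, 6 | 5, 7 | 4 |
| Hong Kong | 3, 4, 7 | 1, 2, 5, 6 | 2 |

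Four of six strains are affected, with 3 + 4 + 4 + 2 = 13 matched pairs.

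**Step 2. Closed form with equal slopes.** Let k of 7 equal-sized arms encode the strain, and let r be the residual SD in non-encoding arms divided by that in encoding arms. The pooled variance, in units of the encoding-arm variance, is (k + (7 − k)r²)/7. The true variance of a contrast between two encoding arms uses 1 in its place. So

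- reported/true standard error: w = √[(k + (7 − k)r²)/7]
- large-sample coverage of the nominal 95% interval: 2Φ(1.96w) − 1

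The documents give no value for r, so a range is assumed. Example, Hong Kong (k = 3) at r = 0.4: w = √[(3 + 4 × 0.16)/7] = √0.52 = 0.721, and coverage = 2Φ(1.413) − 1 = 84.2%.

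| r | Hong Kong (k = 3): w, coverage | B/Yamagata (k = 4): w, coverage | Darwin, Newcastle (k = 5): w, coverage |
|---|---|---|---|
| 0.4 | 0.721, 84.2% | 0.800, 88.3% | 0.872, 91.2% |
| 0.6 | 0.796, 88.1% | 0.852, 90.5% | 0.904, 92.4% |
| 0.8 | 0.891, 91.9% | 0.920, 92.9% | 0.947, 93.7% |
| 1.0 | 1.000, 95.0% | 1.000, 95.0% | 1.000, 95.0% |
| 1.25 | 1.150, 97.6% | 1.114, 97.1% | 1.077, 96.5% |

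On the titer scale, assume an encoding-arm residual SD of 1.5 log2 units and 95 evaluable per arm. The correct half-width is 1.96 × 1.5 × √(2/95) = 0.427 log2, a factor of 2^0.427 = 1.34 either side of the GMTR. At r = 0.4 the Hong Kong interval would show 0.721 × 0.427 = 0.308 log2, a factor of 1.24.

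**Step 3. Simulation with unequal slopes.** Assumptions: 95 per arm, encoding SD 1.5 with slope 0.55; non-encoding SD 0.6 / 0.9 / 1.2 (r = 0.4 / 0.6 / 0.8) with slope 0.95 / 0.85 / 0.70. Over repeated runs of this setting, seven-arm coverage was 84-85 / 87-88 / 91-92% for Hong Kong, 88-90 / 90-91 / 92-93% for B/Yamagata and 91-92 / 92-93 / 93-94% for Darwin and Newcastle. Fitting only the two arms compared gave 94-96% throughout.

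**Step 4. The slope on its own.** If the slopes differ by d and the baseline SD is s (in encoding-arm residual SDs), the pooled slope misses the encoding slope by b = d(7 − k)/7. The residual variance becomes 1 + (bs)² in encoding arms and r² + ((d − b)s)² elsewhere. At r = 1, d = 0.5, s = 1 the pooled variance is 1 + 0.25 × k(7 − k)/49. The seven-arm interval is then √1.051 = 1.025 times (k = 5) or √1.061 = 1.030 times (k = 3 or 4) as wide as one from the encoding arms only. So pooling the slope adds residual variance.

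Width and coverage can part company. At r = 0.9, d = 0.7, s = 1.5 the seven-arm interval is 1.08-1.09 times as wide as the encoding-arms interval. Coverage is 93.0% for Hong Kong, 94.9% for B/Yamagata and 95.8% for Darwin and Newcastle.

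**Step 5. After the change.** Restricting the model to the encoding arms, or to the pair, gave simulated coverage of 94.3-95.9% in every setting tried (100 per arm). At r = 1 with equal slopes the seven-arm interval was 0.997-0.999 times as wide, so the lost degrees of freedom cost less than 1%.

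**The case against.** A reader might infer that the intervals for these four strains simply are too narrow. The documents do not support that. They give no titer SD, slope or cross-reactivity figure, and at r = 1 with equal slopes the intervals are right, while at r above 1 they are too wide. Every arm also contains at least one A/H3N2 antigen, so no arm is unstimulated for Darwin, Newcastle or Hong Kong. Protocol 4.2 says the added strains were chosen "for their antigenic distance compared to the Darwin strain contained in the 2022/2023 NH vaccine composition", but the same sentence also cites breadth across the H3N2 family. Cross-response could bring r close to 1 for three of the four strains. The premise of low scatter is most plausible for B/Yamagata. Only one candidate encodes that strain, and the protocol drops it from the others because of limited circulation, so it carries limited weight in choosing a lead.

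A reader might also infer that the common slope contributes to narrow intervals. Step 4 shows that by itself it slightly widens them.

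The consequences are limited too. There is no hypothesis, margin or success rule, and GMTR appears among the exploratory endpoints (Protocol Table 2, SAP 3.3). Randomization keeps the matched GMTR essentially unbiased. Each arm's GMT and GMFR also carry their own t-based intervals, so readers would see the spread by arm. Finally, the seven-arm fit is inferred, not stated.

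All of this stands as a limit on the direction and size of the effect. It does not show that the stated coverage is assured. The plan reports "will be estimated from the ANCOVA model, with 95% CI provided accordingly", and that interval depends on an equal-variance assumption that the plan does not mention.

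**Conclusion.** The point holds in conditional form. On the natural reading of SAP 6.5.2 and 6.6, the 13 matched GMTR intervals for B/Yamagata, Darwin, Newcastle and Hong Kong have their stated coverage only if encoding and non-encoding arms share the same residual scatter.

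Less scatter in non-encoding arms is plausible but undocumented. Under assumed SD ratios of 0.4 to 0.8, coverage falls to about 84-92% for Hong Kong, 88-93% for B/Yamagata and 91-94% for Darwin and Newcastle. More scatter makes the intervals too wide: at a ratio of 1.25 with equal slopes, coverage is 96.5-97.6%.

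Only the intervals are at issue. The estimates remain essentially unbiased, and A/H1N1 and B/Victoria are not affected. This is a cheap improvement to a descriptive analysis, not a demonstrated error in its results.

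**What to change.** In SAP 6.5.2 and 6.6, state for each strain which arms enter the ANCOVA, and choose one of the following:

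- Estimate the matched GMTRs from an ANCOVA restricted to the arms that encode the strain, or to the pair compared, with the same covariates as now.
- Keep all seven arms but allow arm-specific residual variance (for example PROC MIXED with REPEATED / GROUP=arm and Satterthwaite or Kenward-Roger degrees of freedom). If arm-by-baseline slopes are added, read the GMTR at the overall mean baseline.

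Table 6 also marks unmatched pairs, so if the encoding-arms model is chosen, the SAP should say which model serves those.

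The cost is SAP wording and a small programming change. Intervals are less than about 1% wider when the variances are equal. Pairwise fits give an arm slightly different adjusted means from one comparison to the next, which the encoding-arms model largely avoids. Arm-specific slopes make the GMTR depend on the baseline at which it is read, so that value must be fixed in advance.

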In addition to the information presented in the SAP section of the protocol (Section 9), which provides the principal features of analyses for this study, this SAP provides statistical analysis details and data derivations. It also documents modifications or additions to the analysis plan that are not “principal” in nature and result from information that was not available at the time of protocol finalization. If the methods in this SAP differ from the methods described in the protocol, the SAP will prevail.

The SAP will be finalized and approved preferably prior to first patient first visit but no later than before receipt of the first live data.

The study is a Phase 1/2, randomized, open-label study to evaluate the safety, reactogenicity, and immunogenicity of mRNA-1011.1, mRNA-1011.2, and mRNA-1012.1 candidate seasonal influenza vaccines in healthy adults 50 to 75 years of age.

Parexel Biostatistics and Programming team, designee of Moderna Biostatistics and Programming department, will perform the statistical analysis using SAS Version 9.4 or higher to generate all statistical outputs (tables, figures, listings, and datasets).

2. Study Objectives

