6.2.2. Demographics and Baseline Characteristics

Descriptive statistics will be calculated for the following continuous demographic and baseline characteristics: age (years), sex, race, ethnicity, weight (kg), height (cm), and body mass index (BMI) (kg/m^2). Summaries will be presented by vaccination group and overall based on the Safety Set and FAS.

In addition, randomized participants with any inclusion or exclusion criteria deviations will be provided in a listing.

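### The titer ANCOVA is valid as written, but adding age as a covariate would cost almost nothing and might tighten the GMTR intervals slightly

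*SAP*

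**What the plan says.** SAP 6.5.2 models log titer at Day 29 on vaccination group, with prior-season vaccination status and "the log-transformed baseline antibody titer as the covariates". SAP 6.6 uses the same structure for Day 29 and Day 181, "with the treatment group as the explanatory variable and influenza vaccination status in the previous influenza season", plus log baseline titer. Protocol 9.5.3 is shorter still and promises GMTRs only "after adjustment of baseline titers, at each available timepoint".

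Age appears in none of these models. It is collected: SAP 6.2.2 summarizes "continuous demographic and baseline characteristics: age (years), sex, race, ethnicity" by vaccination group and overall, in the Safety Set and the FAS. Randomization is stratified by prior-season vaccination status alone (Protocol 6.2, SAP 4.4). The only subgroup factor in SAP 6.7 is that same status, and it applies to the primary (safety) endpoints. Eligible participants are aged 50 to 75, and Protocol 4.2 comments that "This broad age range allows inclusion of older adults".

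**The concern.** Baseline covariates that predict the outcome reduce residual variance in an ANCOVA and condition the estimate on chance differences between arms. Age is an obvious candidate: it is already recorded, spans 25 years, and is not balanced by the randomization scheme. If it predicts post-vaccination titer beyond what baseline titer and prior vaccination explain, that variation now sits in the residual and widens each GMTR interval.

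The arms are also reused. SAP Table 6 lists 15 pairwise comparisons: three mRNA-1010 controls against four candidate arms, plus mRNA-1011.2 against the other three. Each mRNA-1010 control enters four comparisons and mRNA-1011.2 enters six. An arm that happened to be older or younger would carry that into every ratio it enters. The ratios matter because the study is meant to support the choice of a lead candidate (Protocol 2.1).

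**Working it through.** **The plan's own figure.** The only design calculation in the documents is the chance of seeing at least one adverse event in 100 participants, 1 − (1 − p)^100. For p = 1%, 2%, 3% and 4% it gives 63.4%, 86.7%, 95.2% and 98.3%, as stated in SAP Table 2. It does not bear on titers; no precision or power figure is given for any GMTR.

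**Inputs from the documents.** About 700 participants in 7 arms of about 100 (SAP 4.3); two covariates in the model; 95% intervals (SAP 6.5.2). Residual degrees of freedom are 700 − 7 − 2 = 691 without age and 690 with it. The PP Set will be somewhat smaller, which hardly changes the ratios below.

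**Assumed inputs.** The documents give neither a titer SD nor any age–titer association within 50–75. I take a partial correlation r between age and log post-vaccination titer (given arm, prior vaccination and baseline titer) of 0 to 0.3, with 0.4 as an outer value; a residual SD of 1 to 2 log2 units; and an age SD of 5 to 7.2 years, where 7.2 = 25/√12 is a uniform spread over 50–75.

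**Interval width.** The ratio of widths, with age to without, is √[(1 − r²)(1 + 1/690)]. The second factor allows for chance correlation of age with arm; the change in the t quantile is negligible. The equivalent gain per arm is 100/[(1 − r²)(1 + 1/690)] − 100.

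**Chance imbalance.** Between two arms of 100, 95% of differences in mean age lie within 1.96 × √(2/100) = 0.277 SD, or 1.4 to 2.0 years. At that limit, a GMTR from the model without age shifts by a factor of 2^(0.277 × r × residual SD).

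| r | Width ratio | Participants gained per arm | GMTR shift at the 95% limit (residual SD 1 to 2) |
|---|---|---|---|
| 0 | 1.0007 | −0.1 | none |
| 0.1 | 0.9957 | 0.9 | 1.02 to 1.04 |
| 0.2 | 0.9805 | 4.0 | 1.04 to 1.08 |
| 0.3 | 0.9546 | 9.7 | 1.06 to 1.12 |
| 0.4 | 0.9172 | 18.9 | 1.08 to 1.17 |

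For scale, the GMTR interval without age has a half-width factor of 1.21 (SD 1) to 1.47 (SD 2). On the log scale, the shift at the 95% limit divided by the half-width is close to r itself, so an unlucky imbalance moves the estimate by roughly 10% to 30% of the half-width for r = 0.1 to 0.3.

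**Simulation check.** With 1,000 simulated trials at each r, fitting both models, mean width ratios were 1.0007, 0.996, 0.981 and 0.955 for r = 0, 0.1, 0.2 and 0.3. Coverage of the 95% interval without age was 0.954, 0.949, 0.951 and 0.955. Leaving age out does not damage coverage, because the ordinary interval already allows for chance imbalance.

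**The case against.** The case for leaving the model alone is strong. It already contains the baseline value of the outcome and the only stratification factor, and so does more than Protocol 9.5.3 promises. No passage says that age predicts titer within 50–75. Protocol 2.2.2 reports HAI responses in younger and older adults without sizing any gradient; the one age difference it states concerns solicited reactions, under 50 against 50 and over. Immunogenicity is secondary and descriptive, with no hypothesis, margin or power target, so no decision rule turns on an interval a few percent narrower. Age is tabulated by arm, so a marked imbalance would be visible. The same argument could also be made for sex or BMI.

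Most of this stands, and it limits the size of the point. It does not show a downside to the extra term. Seeing an imbalance in a table is not the same as having a planned adjustment for it, and a covariate added afterwards in an open-label study would look data-driven. Choosing age over sex or BMI is a judgement, prompted by a deliberately wide age range and a rationale centred on older adults; it does not rest on evidence of a larger effect.

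A reader might infer more: that material precision is being thrown away, that the ratios are biased by age, or that Protocol 4.2 itself ties antibody response to age. The documents support none of these. The sentence in Protocol 4.2 gives a reason for enrolling older adults, namely their comorbidities and worse outcomes from influenza. Randomization protects against bias on average. The PP Set is formed after randomization, so that protection is exact only for the randomized groups, but nothing in the documents suggests that exclusions would depend on age and arm together.

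**Conclusion.** The ANCOVA is sound and no stated figure is wrong. Including age is a small optional improvement with an asymmetric trade: about 0.07% wider intervals if age has no residual association with titer, and about 0.4% to 4.5% narrower on the log scale if the partial correlation is 0.1 to 0.3, worth roughly 1 to 10 participants per arm. It also conditions each ratio on chance age differences. The gain rests wholly on that assumed correlation, and on an age effect that is roughly linear and common to all arms. The negligible cost does not depend on the correlation.

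**What to change.** Add age in years, as a continuous covariate, to the ANCOVA in SAP 6.5.2 and 6.6, beside log baseline titer and prior-season vaccination status. Do this when the SAP is finalized, which SAP section 1 requires before the first live data are received. If live data have already arrived, keep the present model as the main analysis and pre-specify the model with age as a sensitivity analysis.

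The cost is one model term and one of about 691 residual degrees of freedom. No new data, visits or samples are needed.

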4.3. Sample Size and Power

Approximately 700 participants will be randomized in this study, with approximately 100 participants into each of Vaccination Groups 1-7 (≥ 50 to ≤ 75 years of age). Details regarding the number of participants in each vaccination group are presented in [Table 1](#). The probability of AEs based on sample size is presented in [Table 2](#). With 100 participants in each group receiving the study intervention, there is an approximately 87% probability to observe at least 1 participant with an AE if the true incidence of the AE is 2%; if the true incidence rate is 3%, then the probability to observe an AE is approximately 95%.

Table 2: Probability of AEs Based on Sample Size

n	True AE Rate	Probability of 0 AE	Probability of at Least 1 AE Observed
100	1.0%	36.6%	63.4%
100	2.0%	13.3%	86.7%
100	3.0%	4.8%	95.2%
100	4.0%	1.7%	98.3%

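### Day 29 seroconversion differences are not adjusted for baseline HAI titer, unlike the GMTRs for the same pairs, which costs some precision

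*SAP*

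**What the plan says.** SAP 6.5.2 plans two between-group contrasts at Day 29 for every pair in Table 6, which holds 4 + 4 + 4 + 3 = 15 pairs.

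- **GMTR.** The ratio "between the two vaccination groups at Day 29 will be estimated from the ANCOVA model". That model has vaccination group, prior-season vaccination status "and the log-transformed baseline antibody titer as the covariates". Protocol 9.5.3 likewise asks for GMTRs "after adjustment of baseline titers, at each available timepoint".
- **Seroconversion.** The SAP states that "the difference of seroconversion rates between the two vaccination groups at Day 29 for each applicable pair will be provided along with 95% CIs", by the Miettinen-Nurminen method. No covariate and no stratum is named.

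A participant who starts below 1:10 seroconverts by reaching 1:40. One who starts at 1:10 or above needs "a minimum 4-fold rise in post-vaccination HAI antibody titer".

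No other section supplies an adjusted version. The exploratory ANCOVA in SAP 6.6 is for titers only. The subgroup analysis by prior-season vaccination in SAP 6.7 covers only the primary (safety) endpoints. Randomization is stratified by prior-season vaccination (SAP 4.4), not by titer. Seroconversion is a secondary endpoint (SAP 3.2) under an objective that compares the candidates with the mRNA-1010 controls (SAP 2.2). The GMTR is listed as exploratory (SAP 3.3), although 6.5.2 estimates it alongside.

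**The concern.** Measuring each person against their own baseline does not make the chance of seroconverting independent of that baseline. The 4-fold rule works like a dichotomised change score. If the Day 29 titer rises less than one-for-one with baseline, people who start high meet the rule less often. With about 100 per arm and a separate baseline for each strain, some chance imbalance is expected across the pair-by-strain contrasts. The crude difference then leans toward the arm with the lower baseline, while the GMTR for the same pair has that component removed.

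At stake are the precision of a comparative secondary result and its sensitivity to an imbalance that the data already in hand could account for. The study's purpose is to help choose which candidate moves to pivotal trials, so these differences will be read closely.

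**Working it through.** **1. The plan's own figures.** The only sample-size calculation (SAP 4.3) concerns adverse events: "With 100 participants in each group receiving the study intervention, there is an approximately 87% probability to observe at least 1 participant with an AE" at a true rate of 2%. With 1 − (1 − p)^100, rates of 1%, 2%, 3% and 4% give 63.4%, 86.7%, 95.2% and 98.3%. All four reproduce. The plan gives no precision or power for seroconversion.

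**2. Precision of the crude difference.** Miettinen-Nurminen 95% half-widths with equal rates in both arms, in percentage points:

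| Rate | 100 per arm | 90 per arm |
|---|---|---|
| 30% | 12.6 | 13.3 |
| 50% | 13.8 | 14.5 |
| 70% | 12.8 | 13.5 |
| 85% | 10.3 | 11.0 |

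**3. Why baseline still matters.** Let b be log2 baseline titer and let the Day 29 log2 titer be m + s(b − 5) + e. A 4-fold rise needs m + s(b − 5) + e − b ≥ 2, that is, e ≥ 2 − m + 5s + (1 − s)b. Each doubling of baseline raises the bar by (1 − s) log2 units. The dependence vanishes only at s = 1.

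**4. Simulation.** All titer inputs are assumptions, because the documents give none:

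- 100 per arm, with no true difference;
- half of participants vaccinated in the prior season, with a baseline 1 log2 unit higher;
- mean baseline 5 log2, SD 1.2, 1.6 or 2.0;
- slope s of 0.3, 0.5 or 0.7;
- mean Day 29 titer 7 or 8 log2, residual SD 1.3;
- titers on a 2-fold grid, with values below 1:10 set to 1:5;
- 1000 runs for each of the 18 scenarios.

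The SAP rule was applied, which gave seroconversion rates of 55% to 85%. The crude difference was compared with the average of predicted(arm 1) − predicted(arm 0) over all participants, from a logistic model with arm, log2 baseline titer and prior vaccination.

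| Slope | Variance reduction | CI shortening | Shift of crude difference per 1-SD imbalance |
|---|---|---|---|
| 0.3 | 11.6 to 26.6% | 6.0 to 14.3% | 1.8 to 3.5 points |
| 0.5 | 5.2 to 10.5% | 2.6 to 5.4% | 1.0 to 2.4 points |
| 0.7 | −0.1 to 1.6% | −0.1 to 0.8% | 0.4 to 1.0 points |

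Checks on the table:

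- **CI shortening** is 1 − √(1 − variance reduction). At the top, 1 − √0.734 = 14.3%.
- **Shift** is the regression of the crude difference on the imbalance, times the SD of the imbalance. At the top (SD 2.0, s = 0.3, m = 7), 0.144 × 0.243 = 0.035. After adjustment the same product is 0.013 × 0.243 = 0.003, and across all scenarios it stays under 0.4 points.
- **SD of the crude estimate.** At SD 1.2, s = 0.3, m = 7 the rate is 61.1%, and √(2 × 0.611 × 0.389 / 100) = 6.9 points. The simulation gave 6.8.
- **Bias.** The mean crude difference was within 0.4 points of zero. The Monte Carlo standard error is about 0.071/√1000 = 0.2 points.

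**5. Other assumptions.** With baseline GMT 30, baseline SD 1.3 to 1.8 and residual SD 1.4 (2000 runs per scenario), the ratio of adjusted to crude variance was 0.79 to 0.86 at slope 0.3, 0.86 to 0.93 at 0.5, and 0.95 to 0.97 at 0.7. The shift per 1-SD imbalance was 0.2 to 3.0 points. With residual SD 1.5 and a true difference of about 0.16, the ratios were 0.81 to 0.86, 0.93, and 0.97 to 0.98. There the adjusted estimate was unbiased for the same marginal difference.

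**The case against.** The strongest reply is that nothing here is invalid. Seroconversion is already defined participant by participant against baseline, so the comparison does not ignore it. Arms are randomized, so the crude difference is unbiased, and chance imbalance is ordinary sampling error that the interval already covers. A shift of at most 3.5 points is small beside half-widths of 10 to 14 points. The protocol asks for baseline adjustment of GMTRs only, so the SAP does not depart from it. Baseline GMTs will be reported by group, so a reader can see any imbalance. All of this stands, and it limits the point to efficiency.

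Three stronger readings are tempting and are not supported.

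- **Bias.** A reader might infer that the crude differences are biased. Randomization rules that out, and the simulations agree.
- **Power.** A reader might take a generic correlation of 0.5, hence a 25% cut in variance, and read off a gain in power. SAP 4.2 sets no hypotheses, so there is no power target to improve. In the main simulation the correlation of baseline with seroconversion was 0.09 to 0.50 in absolute value, so 0.5 is the most favourable end.
- **Agreement with the GMTR.** A reader might expect adjustment to bring the two results for a pair into line. One is a contrast of mean log titers and the other a dichotomised rise, so they can diverge after identical adjustment. Under the second set of assumptions, their correlation rose from 0.63–0.78 to 0.70–0.79. The two still differed in sign in 11 to 24% of runs after adjustment, against 10 to 25% before.

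The cost argument also has force. A second estimate for 15 pairs across all tested strains adds clutter. Groups 2 to 4 contain no B/Yamagata, so a model for that strain may meet very few seroconverters.

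**Conclusion.** The asymmetry is real: the same pairs and visit get a baseline-adjusted GMTR and an unadjusted seroconversion difference. Its consequence is a modest loss of precision and some sensitivity to chance baseline imbalance, not an error of validity.

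The overall range is a variance reduction of about 0 to 27% and a CI 0 to 14% shorter. It is typically 3 to 5% shorter at slope 0.5, and the gain is negligible near slope 0.7. The shift removed is about 0.2 to 3.5 points per 1-SD imbalance. These figures rest wholly on assumed titer distributions. The main simulation's model also had no indicator for baseline below 1:10, which the proposed model adds. Since the study is descriptive, this is a worthwhile refinement rather than a necessary correction.

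**What to change.** In SAP 6.5.2, keep the Miettinen-Nurminen difference and prespecify a supportive adjusted difference for each Table 6 pair and strain:

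- Fit a logistic regression of Day 29 seroconversion on vaccination group, log2 baseline titer, an indicator for baseline below 1:10 (where the rule changes), and prior-season vaccination status.
- Standardise over the pooled baseline distribution of the two arms, so that the result is a difference in rates on the same scale as the crude one.
- Give a delta-method or bootstrap 95% CI, and name which.
- State in advance when the model is not fitted and only the crude difference is reported. One such rule is fewer than 5 seroconverters or fewer than 5 non-seroconverters in either arm.

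The cost is a paragraph of SAP text, one more column per table and a model-based interval. No new data are needed, because the PP Set already requires baseline and Day 29 samples. Writing it down beforehand matters because the study is open-label, and an adjusted result added later could look chosen from the data.
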